9.0 Research Methods

9.1 Study Design

This is a prospective, mono-country, multi-center study in AS patients treated with adalimumab.

At least 200 subjects will be enrolled at approximately 10 sites.

Physicians will be asked to document on a separate log the number of patients who are possible to participate in this study. Presence or absence of EAMs and decision to participate will be collected.

The baseline assessment should be performed prior to the first dose of adalimumab (Visit1). Study visits will be conducted at 12, 28, 36 and 52 week after baseline. All subjects will have one Follow-up approximately 30days after the last dose of adalimumab.

Primary Endpoint:

- The frequency of EAMs of interest at baseline: peripheral arthritis, enthesitis and dactylitis

Secondary Endpoints:

- The percentage of patients with 50% improvement of baseline BASDAI (BASDAI 50) at week 12, 28, 36, and 52
- The change of MASES (Maastricht Ankylosing Spondylitis Enthesitis Score) from baseline to week 12, 28, 36, and 52 in patients who had enthesitis at baseline
- The percentage of patients who have enthesitis of the plantar fascia from baseline to week 12, 28, 36 and 52.
- The change of dactylitis score from baseline to week 12, 28, 36 and 52 in patients who had dactylitis at baseline.
- The change of tender and swollen joint counts (TJC, 0-46; SJC, 0-44) from baseline to week 12, 28, 36 and 52 in patients who had peripheral arthritis (≥ 1 swollen joint) at baseline.

The prescription of adalimumab is at the discretion of the physician in accordance with clinical practice and label, is made independently from this study and precedes the decision to offer the patient the opportunity to participate in this study.

9.2 Setting**9.2.1 Selection of Study Population**

Subject will be adults with AS who meet the eligibility criteria.

Inclusion Criteria

- Subject must be an adult ≥ 19 years

- Subject has been diagnosed with ankylosing spondylitis according to the 1984 modified New York criteria for at least 3months
- Subject has active disease defined by a BASDAI score ≥ 4 despite treatment with at least 2 NSAIDs based on Korea AS reimbursement guideline
- Subject is eligible for adalimumab in daily rheumatologic practice
- Subject must provide written authorization form to use personal and/or health data prior to the entry into the study

Exclusion Criteria

- Female subjects who are pregnant or breast feeding
- Subject applies contraindication to any anti-TNF agent
- Subject is participating in other clinical trials

9.2.2 Drop-Out Subjects

Once a subject is dropped out from the study, no further information for that subject will be collected. However, the reason for drop-out will be reported and serious adverse events will be reported to AbbVie until 30 days following the intake of the last dose of adalimumab.

Subjects will be dropped out from the study:

- 1) If the subjects choose to withdraw from the study
- 2) Where ethical or practical conflicts hinder the procedure of the study, and such cases will be determined based on the investigator's judgment
- 3) In case of Adalimumab discontinuation at any point during study period

9.2.3 Investigator Selection Criteria

The rheumatologist will be selected based on the following criteria:

- Those who work in hospitals that have sufficient numbers of eligible patients.
- Those who agree to devote adequate time to conduct the study in accordance with the protocol.
- Those who will report any serious adverse events in patients using an AbbVie product to AbbVie in accordance with the protocol.

9.3 Variables

Participating subjects will be followed up at week 12, 28, 36, and 52 for 12 months after baseline. At baseline, demographics, disease and medication related data, the presence of extra-axial symptoms such as peripheral arthritis, enthesitis and dactylitis will be collected.

On every follow-up visit, BASDAI 50 will be measured to observe the effectiveness of AS. Also, the change of MASES, TJC_s (0 to 46), SJC_s (0 to 44), Dactylitis score and the presence of plantar fascia will be evaluated to investigate the effectiveness of adalimumab on EAMs.

After baseline visit, if subjects have extra-axial symptoms other than Enthesitis, Peripheral arthritis and Dactylitis, relevant data will be collected.

Enthesitis is defined as at least 1 inflamed enthesis in the Maastricht Ankylosing Spondylitis Enthesitis Score (MASES, 0 to 13) or of the plantar fascia of the foot. Peripheral arthritis is defined as at least 1 of swollen joint counts (SJC, 0 to 44, excluding hip joints). Dactylitis will be measured by a simple count of dactylitic digits.

Patients will be administered adalimumab 40 mg every other week in addition to their preexisting anti-rheumatic treatment for a study period of 1 year as per Korean AS reimbursement guideline.

In the event of Adalimumab discontinuation, the reason for discontinuation will be collected. If the reason for treatment discontinuation is due to an adverse event, the event will be collected.

The following variables will be collected at baseline, and every follow-up visit thereafter during the study period.

Baseline

- 1) Demographics: Age, Gender, Family History of AS, Co-morbidity
- 2) Previous AS-related medication (medication, dosage)
- 3) Concomitant medication
- 4) BASDAI 50
- 5) Extra-axial symptoms: Enthesitis, Peripheral arthritis and Dactylitis (presence or absence)
- 6) Extra-axial symptoms assessment: MASES, enthesitis of the plantar fascia, TJC^s and SJC^s, Counts of dactylitic digits
- 7) Adalimumab administration

Week 12, 28, 36 and 52 after baseline

**Window period for each follow up visit will be ± 4 weeks.*

- 1) BASDAI 50

- 2) Extra-axial symptom assessment: MASES, enthesitis of the plantar fascia, TJC^s and SJC^s, Counts of dactylitic digits
- 3) The change of AS-related medication (If applicable)
- 4) Extra-axial symptoms excluding Enthesitis, Peripheral arthritis and Dactylitis (If applicable, such as IBD, uveitis, etc.)

9.4 Data Sources

The investigator should maintain source documents for each subject in the study, consisting of medical records containing demographic data, and other information to be collected.

Case Report Forms will be supplied by AbbVie, and used to transmit the collected information during this study to AbbVie.

Case report forms will include patient demographic information, e.g., gender, age, unique patient study number, family history of AS, co-morbidity and the information to be evaluated according to the study protocol. Case report forms will maintain patient confidentiality, e.g., patient names must not be collected and full date of birth must not be collected (age is acceptable). The investigator or staff under his/her supervision must complete the case report forms, and neither AbbVie nor any agents acting on behalf of AbbVie may complete the case report forms.

9.5 Study Size

The primary endpoint of this study is to investigate the frequency of extra-axial symptoms such as peripheral arthritis, enthesitis and dactylitis in eligible Korean AS patients.

With reference to a study in Korean AS patients^{(1),(3)}, peripheral arthritis, enthesitis and dactylitis were found in 70%, 53% and 1% in AS patients, respectively. We calculated sample size based on the expected frequency of peripheral arthritis and enthesitis.

By assuming 95% confidence interval and 15% confidence interval width, the sample size is estimated at 144 and 171 for peripheral arthritis and enthesitis, respectively. Considering 20% of drop-out rate, about 200 patients will be recruited.

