- To observe the effectiveness of adalimumab on AS spinal disease activity in routine clinical practice
- To investigate the effectiveness of adalimumab on EAMs in routine clinical practice

Study Design:

This is a prospective, mono-country, multi-center study in AS patients treated with adalimumab. At least 200 subjects will be enrolled at approximately 10 sites.

The baseline assessment should be performed prior to the first dose of adalimumab (Visit1). Study visits will be conducted at 12, 28, 36 and 52 week after baseline. All subjects will have one Follow-up approximately 30days after the last dose of adalimumab.

The prescription of adalimumab is at the discretion of the physician in accordance with clinical practice and label, is made independently from this study and precedes the decision to offer the patient the opportunity to participate in this study.

Primary Endpoint:

The frequency of EAMs of interest at baseline: peripheral arthritis, enthesitis and dactylitis

Secondary Endpoints:

- The percentage of patients with 50% improvement of baseline BASDAI (BASDAI 50) at week 12, 28, 36, and 52
- The change of MASES (Maastricht Ankylosing Spondylitis Enthesitis Score) from baseline to week 12, 28, 36, and 52 in patients who had enthesitis at baseline
- The percentage of patients who have enthesitis of the plantar fascia from baseline to week 12, 28, 36 and 52.
- The change of dactylitis score from baseline to week 12, 28, 36 and 52 in patients who had dactylitis at baseline.
- The change of tender and swollen joint counts (TJC, 0-46; SJC, 0-44) from baseline to week 12, 28, 36 and 52 in patients who had peripheral arthritis (≥ 1 swollen joint) at baseline.

Population:

Subject will be adults with AS who meet the eligibility criteria.

Inclusion Criteria

- Subject must be an adult ≥ 19 years
- Subject has been diagnosed with ankylosing spondylitis according to the 1984 modified New York criteria for at least 3months
- Subject has active disease defined by a BASDAI score ≥ 4 despite treatment with at least 2 NSAIDs based on Korea AS reimbursement guideline.
- Subject is eligible for adalimumab in daily rheumatologic practice
- Subject must provide written authorization form to use personal and/or health data prior to the entry into the study.

Exclusion Criteria

- Female subjects who are pregnant or breast feeding

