9.7 Data Analysis

The study population will be classified by ITT (Intention-To-Treat) set and PP (Per-Protocol) set.

- ITT set: The ITT set will consist of those patients who have received at least one adalimumab treatment and have assessed EAMs at baseline.

- PP set: The PP set will consist of those patients who meet inclusion/exclusion criteria and complete the study without any major protocol deviation of the patients included in the ITT set.

General Considerations

Continuous variables will be described with the number of patients, arithmetic mean, standard deviation, median, minimum, and maximum. For categorical variables, the frequency and proportion will be presented. The values such as arithmetic mean, standard deviation, and proportion will be rounded to two decimal places. If the observation value is missing value, it will be treated as a missing value in the analysis.

Baseline Characteristics including demographics

Descriptive statistics will be used to present variables regarding demographics and disease/medication related data. Continuous variables will be described with the number of patients, arithmetic mean, standard deviation, median, minimum and maximum. For categorical variables, the frequency and proportion will be presented. The values such as arithmetic mean, standard deviation, and proportion will be rounded to two decimal places.

If the observation value is missing value, it will be treated as a missing value in the analysis. Statistical analyses will be performed using SAS V9.2 or higher.

Primary Endpoint:

The frequency of EAMs of interest at baseline: peripheral arthritis, enthesitis and dactylitis

-The frequency and the proportion of patients who are having peripheral arthritis, enthesitis or dactylitis in Korean AS patients at baseline will be presented, and 95% confidence intervals will be calculated.

Secondary Endpoints:

- The percentage of patients with 50% improvement of baseline BASDAI (BASDAI 50) at week 12, 28, 36, and 52
 - The frequency and the proportion of patients with 50% improvement of baseline BASDAI at week 12, 28, 36, 52 will be presented.
- The change of MASES (Maastricht Ankylosing Spondylitis Enthesitis Score) from baseline to week 12, 28, 36, and 52 in patients who had enthesitis at baseline
 - The descriptive statistics (the number of patients, mean, standard deviation, median, min, max) for MASES according to study visit and the change from baseline at week 12, 28, 36, 52 will be presented.

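### Recruiting 200 with 20% drop-out leaves 160, not the 171 stated for enthesitis, and follow-up drop-out does not affect a baseline endpoint in the ITT set

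*Combined protocol and SAP*

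**What the plan says.** Section 9.5 (Study Size), repeated in the abstract, takes its planning frequencies from earlier work: "peripheral arthritis, enthesitis and dactylitis were found in 70%, 53% and 1% in AS patients, respectively". It sets a 95% confidence interval with a width of 15% and concludes that "the sample size is estimated at 144 and 171 for peripheral arthritis and enthesitis, respectively". The recruitment figure follows: "Considering 20% of drop-out rate, about 200 patients will be recruited". The design paragraphs of the abstract and Section 9.1 express it as a minimum: "At least 200 subjects will be enrolled at approximately 10 sites".

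The primary endpoint is the frequency of peripheral arthritis, enthesitis and dactylitis at baseline. Section 9.1 places the baseline assessment before the first adalimumab dose. Section 9.7 defines two analysis sets:

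- ITT: "The ITT set will consist of those patients who have received at least one adalimumab treatment and have assessed EAMs at baseline".
- PP: "The PP set will consist of those patients who meet inclusion/exclusion criteria and complete the study without any major protocol deviation".

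For the primary endpoint, Section 9.7 says only that the frequency and proportion "at baseline will be presented, and 95% confidence intervals will be calculated". It names neither the analysis set nor the interval method. Under Section 9.2.2, dropping out ends further data collection; nothing there removes data already collected.

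**The concern.** There are two separate problems with the drop-out step.

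1. **Arithmetic.** The text says both manifestations were used for sizing, so the larger requirement, 171, governs. A recruitment figure that allows for 20% loss should leave at least 171 after that loss. 200 does not.
2. **Relevance.** The endpoint is complete before treatment starts. A patient who leaves at week 12 or week 36 has already contributed to it and remains in the ITT set. For the primary endpoint, follow-up loss reduces only the PP set of completers.

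The study is descriptive, with no hypothesis test and no power calculation, so sample size and interval width are the only statistical properties it plans for. As written, a reader cannot tell which set the 15-point width refers to, and the answer for enthesitis depends on it.

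**Working it through.** **Inputs (Section 9.5):** p = 0.70 (peripheral arthritis), p = 0.53 (enthesitis), 95% confidence, full width 0.15 (half-width 0.075), drop-out 20%, recruitment 200.

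**1. Reproduce the plan's 144 and 171.** Wald interval, n = 1.96² × p(1 − p) / 0.075²:

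- p = 0.70: 143.4, rounded up to 144.
- p = 0.53: 170.1, rounded up to 171.

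Both match, so the planning method was Wald with a total width of 15 points.

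**2. Drop-out step.**

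- 200 × 0.80 = 160. This is above 144 but below 171.
- Enthesitis: 171 / 0.80 = 213.75, so 214.
- Peripheral arthritis: 144 / 0.80 = 180, so 200 is enough at the planning value of 70%.
- Largest loss at which 200 still leaves 171: 1 − 171/200 = 14.5%, or 29 patients.

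A possible route to the stated figure is 171 × 1.20 = 205.2, rounded to about 200. That inflates the wrong way: even 205 × 0.80 = 164 is below 171.

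**3. Interval widths.** Wald width = 2 × 1.96 × √(p(1 − p)/N). Exact (Clopper-Pearson) widths use 106/200 and 140/200, then 85/160 and 112/160.

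| N | Enthesitis, Wald | Enthesitis, exact | Peripheral arthritis, Wald | Peripheral arthritis, exact |
|---|---|---|---|---|
| 200 | 13.8 | 14.2 | 12.7 | 13.1 |
| 160 | 15.5 | 16.0 | 14.2 | 14.7 |

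(Widths in percentage points; target 15.)

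**4. Who leaves each set.** The ITT set loses only enrolled patients who are never dosed or whose EAMs are not assessed at baseline. It stays at 171 or more unless over 29 of 200 fall into that group. The PP set also loses everyone who does not complete the study, so 20% loss would bring it to 160 or fewer.

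**The case against.** The strongest reply is that this hardly matters. With 200 ITT patients the Wald width is within 15 points at any prevalence: the worst case, p = 0.50, gives 13.9. The requirement that EAMs be assessed at baseline suggests the ITT set was built for this endpoint. The word about and the minimum of 200 leave room for more patients, and on the PP reading the miss is half a point in a study with no decision threshold. All of this stands as a statement about size. It does not make the justification correct. If ITT is intended, follow-up drop-out has no role in the sizing. If PP is intended, 200 is too few for enthesitis at the stated loss. A minimum of 200 also permits stopping at 200.

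Three narrower points:

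- **Secondary endpoints.** Follow-up loss does reduce ITT numbers at weeks 12 to 52. This is correct; the statement that it does not affect the ITT set applies to the baseline primary endpoint only. The 20% figure should therefore remain visible in the plan.
- **Withdrawal before the first dose.** This counts as drop-out under Section 9.2.2 and does remove a patient from ITT. It is the one kind of loss, along with a missing baseline assessment, that the allowance could cover. The plan does not say that 20% refers to it.
- **Planning frequencies.** Section 7.1 gives 70% as an upper figure for peripheral joint involvement and reports 47.1% with a history of peripheral arthritis in a Korean study. At 47.1%, peripheral arthritis would also need 171, and 160 patients would give 15.5 points. So the statement that 200 is enough for peripheral arthritis after 20% loss depends on the plan's own 70%. The shortfall for enthesitis does not depend on it.

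**Conclusion.** The concern holds. The figures 144 and 171 are right, but 200 does not allow for 20% loss from 171: it leaves 160, and 214 would be needed. The allowance is also misplaced, because follow-up drop-out removes nobody from the ITT set for an endpoint measured before the first dose.

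The practical effect is small. In the ITT set 200 patients meet the 15-point target for both manifestations, by either interval method. In a PP set of 160, peripheral arthritis meets it; enthesitis misses by about 0.5 point with Wald intervals and about 1.0 point with exact ones.

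These results assume the plan's frequencies of 70% and 53%. The ITT conclusion also assumes that nearly all enrolled patients are dosed and assessed at baseline. The plan does not assign the primary endpoint to either set, so which result applies is open until it does.

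**What to change.** Keep 200 and change the text in these places:

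- **Section 9.7:** name the ITT set as the analysis set for the baseline primary endpoint, and name the confidence interval method.
- **Section 9.5 and the abstract:** remove the claim that 200 allows for 20% drop-out and replace it with wording such as:

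> The primary endpoint is measured at baseline and analysed in the ITT set. With 200 ITT patients the Wald 95% CI width is about 13.8 points for enthesitis (53%) and 12.7 points for peripheral arthritis (70%). If 20% are excluded from the PP set (N = 160), the widths are about 15.5 and 14.2 points. Exact intervals are slightly wider (about 14.2 and 13.1 points at N = 200).

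This keeps the 20% scenario on record. If it is also the expected loss for the secondary endpoints, say so there. If the sponsor instead intends the 15-point target to hold in the PP set after 20% loss, the recruitment figure consistent with Section 9.5 is 214.

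The recommended change costs wording only and adds no patients.

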9.6 Data Management

Investigator should complete, sign and date the CRFs accurately. All CRFs must be legible and completed in indelible ballpoint ink. Corrections to the CRFs should be made with a single line, be initialed and dated, with the reason for changes given. Data are not to be obliterated by blacking out, correction fluid, or by erasing the original entry.

At the completion of the study, the completed signed and dated case report forms of all enrolled patients should be provided to AbbVie by the investigator. ONLY data specified in the protocol should be collected and submitted to AbbVie.

CRAs or their designees will be responsible to review the collected case report forms for completeness and conclusiveness.

9.7 Data Analysis

The study population will be classified by ITT (Intention-To-Treat) set and PP (Per-Protocol) set.

- ITT set: The ITT set will consist of those patients who have received at least one adalimumab treatment and have assessed EAMs at baseline.

- PP set: The PP set will consist of those patients who meet inclusion/exclusion criteria and complete the study without any major protocol deviation of the patients included in the ITT set.

General Considerations

Continuous variables will be described with the number of patients, arithmetic mean, standard deviation, median, minimum, and maximum. For categorical variables, the frequency and proportion will be presented. The values such as arithmetic mean, standard deviation, and proportion will be rounded to two decimal places. If the observation value is missing value, it will be treated as a missing value in the analysis.

Baseline Characteristics including demographics

Descriptive statistics will be used to present variables regarding demographics and disease/medication related data. Continuous variables will be described with the number of patients, arithmetic mean, standard deviation, median, minimum and maximum. For categorical variables, the frequency and proportion will be presented. The values such as arithmetic mean, standard deviation, and proportion will be rounded to two decimal places.

If the observation value is missing value, it will be treated as a missing value in the analysis. Statistical analyses will be performed using SAS V9.2 or higher.

Primary Endpoint:

The frequency of EAMs of interest at baseline: peripheral arthritis, enthesitis and dactylitis

-The frequency and the proportion of patients who are having peripheral arthritis, enthesitis or dactylitis in Korean AS patients at baseline will be presented, and 95% confidence intervals will be calculated.

Secondary Endpoints:

- The percentage of patients with 50% improvement of baseline BASDAI (BASDAI 50) at week 12, 28, 36, and 52
 - The frequency and the proportion of patients with 50% improvement of baseline BASDAI at week 12, 28, 36, 52 will be presented.
- The change of MASES (Maastricht Ankylosing Spondylitis Enthesitis Score) from baseline to week 12, 28, 36, and 52 in patients who had enthesitis at baseline
 - The descriptive statistics (the number of patients, mean, standard deviation, median, min, max) for MASES according to study visit and the change from baseline at week 12, 28, 36, 52 will be presented.
- The percentage of patients who have enthesitis of the plantar fascia from baseline to week 12, 28, 36 and 52.
 - The frequency and the proportion of patients who have enthesitis of the plantar fascia at week 12, 28, 36, 52 will be presented.
- The change of dactylitis score from baseline to week 12, 28, 36 and 52 in patients who had dactylitis at baseline.
 - The descriptive statistics (the number of patients, mean, standard deviation, median, min, max) for dactylitis score according to study visit and the change from baseline at week 12, 28, 36, 52 will be presented.
- The change of tender and swollen joint counts (TJC, 0-46; SJC, 0-44) from baseline to week 12, 28, 36 and 52 in patients who had peripheral arthritis (≥ 1 swollen joint) at baseline.
 - The descriptive statistics (the number of patients, mean, standard deviation, median, min, max) for tender and swollen joint counts (TJC, 0-46; SJC, 0-44) according to study visit and the change from baseline at week 12, 28, 36, 52 will be presented.

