9.7.1 Safety Analysis

The serious adverse event will be coded by MedDRA (Medical Dictionary for Regulatory Activities).

The cumulative total number and percentage of patients reporting serious adverse event and adverse drug reaction will be tabulated. The reason for treatment discontinuation will also be summarized.

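### BASDAI 50 at weeks 12 to 52 has no stated denominator and will probably describe only patients still on adalimumab, even in the ITT set

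*Combined protocol and SAP*

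**What the plan says.** Section 9.2.2 lists among its reasons for drop-out: "In case of Adalimumab discontinuation at any point during study period". The consequence is given in the same section: "Once a subject is dropped out from the study, no further information for that subject will be collected". The exceptions are the reason for drop-out and serious adverse events up to 30 days after the last dose.

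Section 9.7 defines two analysis sets but assigns neither to any endpoint. The ITT set asks only for one dose and a baseline EAM assessment, so patients who stop early belong to it. The PP set is restricted to those who "complete the study without any major protocol deviation of the patients included in the ITT set" and meet the eligibility criteria.

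For BASDAI 50 the whole analysis is: "The frequency and the proportion of patients with 50% improvement of baseline BASDAI at week 12, 28, 36, 52 will be presented". The general rule for this type of variable is "For categorical variables, the frequency and proportion will be presented", whereas for continuous variables the number of patients is listed explicitly. Missing data are covered by one sentence: "If the observation value is missing value, it will be treated as a missing value in the analysis".

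On discontinuation, Section 9.3 says "In the event of Adalimumab discontinuation, the reason for discontinuation will be collected" and Section 9.7.1 says "The reason for treatment discontinuation will also be summarized". Section 9.9, on limitations, is marked as not applicable.

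**The concern.** These provisions act together. A patient who stops adalimumab has no later BASDAI, the missing value stays missing, and no rule puts the patient back into the denominator. The ITT proportion at a late visit then becomes a proportion among those still on drug. By week 52 the ITT observed cases are close to the completers who make up the PP set, so comparing the two sets would not reveal the problem.

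The first secondary objective is effectiveness on spinal disease activity in routine practice. Stopping treatment is part of what happens in routine practice, and there is no control arm in which similar losses could be seen. If patients who stop respond less often, the reported proportion is too high and can rise from visit to visit only because non-responders leave. Two analysts following Section 9.7 could also report different week-52 figures from the same data.

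**Working it through.** **Step 1: can a patient who stopped have a later BASDAI?** Section 9.3 schedules BASDAI at baseline and at weeks 12, 28, 36 and 52 only. Section 9.1 adds a contact about 30 days after the last dose, but no BASDAI is listed for it. A poor score at a scheduled visit before stopping is kept at that visit. Nothing is recorded for later visits.

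**Step 2: inputs.**
- From Section 9.5: about 200 patients, a 20% drop-out allowance and a requirement of 171 for enthesitis. The 171 reproduces: 1.96² × 0.53 × 0.47 / 0.075² = 170.1, rounded up to 171.
- The 20% is a sample-size allowance with no timing. It is used here as an assumption about loss before week 52.
- The documents give no BASDAI 50 rate. An observed-case rate of 60% is assumed and then varied.
- A drop-out fraction of 1 − 171/200 = 14.5% is the loss that 200 recruits can absorb while keeping 171. It is a scenario, not a forecast. 10% is a further scenario.

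**Step 3: formula.** Let r be the response rate among those observed, d the fraction lost before the visit, and k the response of drop-outs relative to those observed.

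Full-ITT rate = r(1 − d) + k·r·d, so gap = d × (r − k·r).

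**Step 4: results with r = 60%.**

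| d | k = 0 | k = 0.5 | k = 1 |
|---|---|---|---|
| 20% | 48.0% (gap 12.0) | 54.0% (gap 6.0) | 60.0% (gap 0) |
| 14.5% | 51.3% (gap 8.7) | 55.65% (gap 4.35) | 60.0% (gap 0) |
| 10% | 54.0% (gap 6.0) | 57.0% (gap 3.0) | 60.0% (gap 0) |

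The gap should be smaller at week 12, when fewer patients have left.

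**Step 5: in counts, with 200 patients and 20% loss.** Observed-case: 96/160 = 60.0% (Wilson 95% CI 52.3 to 67.3). Full ITT with missing as non-response: 96/200 = 48.0% (41.2 to 54.9). If all 40 missing patients had responded: 136/200 = 68.0%.

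**Step 6: other observed rates, d = 20%, k = 0.** Observed rates of 50, 60, 70 and 80% become 40, 48, 56 and 64%, a gap of 10 to 16 points.

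**Step 7: a rise produced by drop-out alone.** Hold 96 responders fixed and let only non-responders leave, cumulatively 5, 10, 15 and 20% at weeks 12, 28, 36 and 52 (assumed timing, extreme case). The observed-case proportion runs 96/190 = 50.5%, 96/180 = 53.3%, 96/170 = 56.5%, 96/160 = 60.0%, although no patient's status changes.

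**The case against.** The strongest objection is that the remedy can err as far as the problem does. If drop-outs would have responded like everyone else (k = 1, d = 20%), counting them as failures reports 48% where 60% would have been seen, 12 points too low. Section 9.2.2 also allows drop-out by patient choice or for practical reasons, which need not reflect lack of effect. An on-treatment description is a legitimate target if it is labelled as one. This stands, and it is why both figures are needed: one gives response among those still treated, the other gives patients treated and responding out of all who started.

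Second, a denominator over all ITT patients is not excluded by the text. That is correct, and it is why the conclusion says probably. The missing-value sentence still points to observed cases, and one sentence from the sponsor would settle it.

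Third, a reader given both a frequency and a proportion can recover the denominator (96 and 60.00% imply 160) and divide by the ITT total instead. This is possible, but it leaves the reader to define the analysis, and the printed percentage is the one that will be cited. Reasons for discontinuation are summarised separately, and no planned table joins them to response by visit.

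Finally, this is a descriptive secondary endpoint with no test, and the documents do not show the direction or size of any bias. Both points are true and limit the severity. A descriptive proportion still needs a defined denominator.

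**Conclusion.** The concern holds and should be fixed. As written, the plan leaves the BASDAI 50 denominator open and, on its own missing-value rule, most probably yields an on-treatment proportion at each visit, whichever analysis set is used. With an assumed 60% observed response and 20% drop-out, the difference from a full-ITT figure is between 0 and 12 points, depending on how drop-outs would have responded; with 10% drop-out it is between 0 and 6. The certain part is the missing denominator and the absence of a rule for stoppers. The overstatement is conditional on stoppers responding less often. The primary endpoint, EAM frequency at baseline, is untouched.

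**What to change.** In Section 9.7, name the analysis set and denominator for BASDAI 50 at each visit, and report two figures:

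- **Full ITT:** responders over all ITT patients, with those who discontinued adalimumab or have no BASDAI at that visit counted as non-responders, and a 95% CI.
- **Observed case:** responders over patients assessed at that visit, labelled as on-treatment, with its n.

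For the change endpoints (MASES, dactylitis, joint counts), where n is already planned, add the baseline mean of the patients contributing at each visit, so that a shift in who remains can be seen. The plantar-fascia percentage falls under the same missing-value rule, so its denominator and observed n should be stated too.

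The cost is SAP wording and one extra table. Discontinuation and its reason are already collected, and the drop-out rule itself need not change. The downside is a lower headline figure that is conservative where loss, or a single missed visit, has nothing to do with effect. Showing both figures lets the reader see this.
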